## Data Analysis

Descriptive statistics will be presented as frequencies and percentages for categorical variables and means and 95% confidence intervals for continuous variables. Differences in baseline demographics and clinical characteristics between groups will be assessed with chi-squared or Fisher's exact tests for categorical variables and independent samples t-tests or single factor ANOVAs (or the nonparametric equivalents) for continuous variables.

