### **Hypothesis**

Null Hypothesis: There is no difference in percentage of patients with sacroiliac joint pain as confirmed by positive anesthetic response (80% relief immediately after injection) to sacroiliac joint steroid injection that achieve moderate or good response (at least 50% improvement in numeric pain rating scale) between those receiving sacroiliac joint corticosteroid injection of 40mg of methylprednisolone and those receiving 10mg of dexamethasone at 4 weeks and 3 months.

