#### Outcome Instruments

*(The baseline examination and all baseline questionnaires will be completed within 2 weeks before the first injection).*

- Location of pain
- Duration of pain
- Demographics
- BMI

Baseline

Follow-up

- Adverse effects

-

Baseline and Follow-up

- NPRS back/buttocks pain (7-day average)
- Oswestry Disability Index (ODI)

Injection Treatment

Based on clinical evaluation patients will be scheduled for a unilateral fluoroscopic guided sacroiliac joint steroid injection. On arrival to the procedure center eligible patients will be enrolled and consented. Patients will then be randomized to receiving sacroiliac joint steroid injection with 1 cc of 2% lidocaine and either 40mg Methylprednisolone (40mg/cc) vs 10mg dexamethasone (10mg/cc)

All injection for this protocol represent different variations all of which fall within the realm of standard of care.

Sacroiliac Joint Steroid injection:

- date of injection recorded
- side of injection (right or left)
- Needle as preferred by physician
- Oral anxiolysis with low dose benzodiazepine as determined by physician
- Local anesthetizing of skin as determined by physician not to exceed 2 cc of superficial 1% lidocaine

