## Power Analysis

A total of 102 patients (51 dexamethasone and 51 methylprednisolone) will provide over 80% power to detect a difference of 20% between groups in the proportion of patients achieving at least moderate improvement on the NPRS using repeated measures binary logistic regression with a level of significance of  $\alpha = 0.05$ . This calculation is based on previous literature showing the proportion of patients achieving at least moderate improvement to be roughly 50% (1). Additionally, this calculation conservatively assumes moderate autocorrelation among the time points and includes an extra 15% to account for potential loss to follow up.

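### No stated outcome analysis uses baseline NPRS or ODI as a covariate; the plan tests baseline differences for significance instead

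*Combined protocol and SAP*

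**What the plan says.** Outcome Instruments lists "NPRS back/buttocks pain (7-day average") and the ODI among the measures taken both at baseline and at follow-up.

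The plan already uses these scores in two ways. Inclusion Criteria sets a floor of 5/10 on baseline NPRS. Specific Aims and Primary Outcomes define NPRS response as a percent improvement (50% or 80%), and aim 3 defines ODI response as a 30% improvement.

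For the analysis itself, Data Analysis offers descriptive statistics and then this: "Differences in baseline demographics and clinical characteristics between groups will be assessed with chi-squared" or Fisher's exact tests for categorical variables, with t-tests, ANOVA or nonparametric equivalents for continuous ones. It names no outcome model. The only model is in Power Analysis, where power is computed "using repeated measures binary logistic regression", with no covariates listed. The closing Analysis section adds a comparative analysis and intention to treat. Study Protocol describes randomisation without stratification factors.

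**The concern.** A baseline significance test asks whether chance could have produced the difference between arms. In a randomised trial that is known in advance. The p-value does not show whether an imbalance matters, because that depends on how strongly the variable predicts outcome. A prespecified covariate addresses the imbalance directly, and the plan has none.

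Two things are at stake in a trial of 51 per arm. Any prognostic information in the baseline scores, beyond their role in the endpoint definitions, goes unused. And with no covariate fixed in advance, a small baseline p-value could prompt an adjustment chosen after seeing the data. The plan does not say that this would happen, but nothing in it prevents it.

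**Working it through.** **Inputs.** From Power Analysis: "A total of 102 patients (51 dexamethasone and 51 methylprednisolone"), a response rate of roughly 50%, a 20-point difference (read as 50% versus 70%), α = 0.05 and 15% loss. Two-sided testing is inferred from the no-difference null in Hypothesis. Retained patients per arm: 51 × 0.85 = 43.4, or 51 / 1.15 = 44.3; 44 is used. The prognostic strength of baseline NPRS and ODI is not given, so it is an assumption shown over a range.

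**The plan's own figure.** For a single time point,

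n = [1.960√(2 × 0.6 × 0.4) + 0.842√(0.5 × 0.5 + 0.7 × 0.3)]² / 0.20² = [1.358 + 0.571]² / 0.04 ≈ 93 per arm.

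With T follow-ups and within-patient correlation ρ, multiply by (1 + (T − 1)ρ)/T. For the two planned follow-ups this gives 47, 61 and 70 per arm at ρ = 0, 0.3 and 0.5. After dividing by 0.85, the totals are 112, 144 and 166. The stated 102 appears with three time points and ρ = 0.2: 93 × 1.4/3 = 43.4, so 44, and 44 × 1.15 = 50.6, so 51 per arm. That is a separate matter. It is noted only because the reference power below is low for that reason and not for want of adjustment.

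**Reference power.** At 44 per arm and one time point: Φ[(0.20√44 − 1.358)/0.678] = Φ(−0.046) = 0.48.

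**Gain from one baseline covariate.** Simulated trials, 44 per arm, latent-normal outcome with shift 0.524 (50% to 70%), logistic Wald test, 4,000 trials per setting:

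| Assumed latent correlation | Unadjusted power | Adjusted power | Gain (points) |
|---|---|---|---|
| 0.3 | 0.476 | 0.495 | 1.9 |
| 0.4 | 0.482 | 0.522 | 4.0 |
| 0.5 | 0.482 | 0.545 | 6.3 |
| 0.6 | 0.490 | 0.583 | 9.3 |

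At zero correlation a separate run gave 0.463 and 0.462, so the extra term cost nothing visible. A smaller repeat (2,500 trials, simulation error about 1 point) gave adjusted power of 53%, 52%, 54% and 57% at 0.3 to 0.6, against 47–49% unadjusted.

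**A second parameterisation.** Covariate strength as an odds ratio per SD, 3,000 trials per setting, 44 per arm. The last column is the movement in the risk difference from a one-standard-error baseline imbalance, √(2/44) = 0.21 SD:

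| OR per SD | Power, unadjusted to adjusted | Variance ratio of risk difference | Shift (points) |
|---|---|---|---|
| 1.00 | 0.495 to 0.495 | 1.01 | 0 |
| 1.28 | 0.479 to 0.489 | 1.00 | 1.3 |
| 1.65 | 0.479 to 0.508 | 0.97 | 2.5 |
| 2.12 | 0.474 to 0.519 | 0.91 | 3.6 |
| 2.72 | 0.471 to 0.548 | 0.85 | 4.4 |

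**Where the primary endpoint is likely to sit.** Response is already scaled by the patient's own baseline NPRS, and baseline is confined to 5–10. A simulation assumed integer scores of 5–10, a pre-truncation mean of 6.5 and SD of 1.2–2.0, a follow-up SD of 2.5 and about 60% response. Raw baseline-to-follow-up correlations of 0 to 0.5 gave absolute latent correlations with 50% response of 0.01 to 0.31. These were near zero at raw correlations of 0.2–0.3 and changed sign across the range. Only a raw correlation of 0.6 gave 0.35–0.43.

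**Chance of a spurious imbalance.** With k independent baseline tests at 0.05, P(at least one significant) = 1 − 0.95^k, which is 34% for k = 8 and 46% for k = 12. The number of tests and their independence are assumptions, since the plan does not itemise its demographic variables.

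**The case against.** The strongest reply is that randomisation already protects the unadjusted comparison. Its standard error allows for chance imbalance, and a one-standard-error imbalance moves the risk difference by only 1.3 to 4.4 points against a 20-point target. The percent-improvement endpoints already bring baseline in, and the gain may be close to nil for the primary outcome. All of this stands, and it limits the point to efficiency and prespecification.

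Several stronger readings are tempting, and the documents do not support them:

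- **That the baseline scores serve only the significance tests.** NPRS sets eligibility, both scores define endpoints, and Data Analysis also plans descriptive statistics.
- **That every outcome depends on baseline NPRS or ODI.** Cessation of pain medication (aim 8) and adverse events (aim 9) are not defined by either score.
- **That adjustment is ruled out.** The plan is silent on covariates.
- **That the precision gain is assured or large.** It is conditional on a correlation that no section reports. The simulations use a single time point and not the repeated measures model that the plan names.

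One qualification cuts the other way. Study Timeline removes patients without 80% immediate relief after randomisation. In the retained set, a true baseline null and a valid unadjusted comparison therefore also assume that this removal does not depend on the steroid given. A baseline p-value would not settle that either.

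The reply leaves two things untouched. Percent change does not remove the association between baseline and response. And the ODI outcome of below 20% (aim 4) is an absolute threshold, so baseline disability is likely to matter most there.

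**Conclusion.** The point holds as a free improvement, with moderate confidence. The plan prespecifies no baseline covariate for any outcome and relies on baseline significance tests that do not serve the purpose. The unadjusted comparison remains valid on average, so this is not a bias.

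For the primary 50% NPRS response, the likely gain is about 0 to 3 power points (assumed latent correlation 0 to 0.3). It rises to about 9 points at 0.6, and is probably largest for ODI below 20%. If the covariate is not prognostic, essentially nothing is lost. These sizes rest on 44 retained per arm, 50% versus 70% response, two-sided α of 0.05, one time point and assumed correlations.

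**What to change.** In Data Analysis:

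1. Delete the between-group baseline tests and present descriptive summaries by arm.
2. State that the repeated measures logistic model for NPRS response includes baseline NPRS, as a continuous term, and that the ODI outcome models include baseline ODI.
3. Report a marginal (standardised) risk difference with its 95% CI beside the odds ratio, because the covariate-adjusted odds ratio is conditional and not directly comparable with the unadjusted one.
4. Keep the unadjusted comparison as a sensitivity analysis.

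The cost is a few sentences of analysis text, settled before outcome data are seen. It needs no new data and no extra patients; the only added work is the marginal estimate.

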### *Follow-up:*

Routine scheduled follow-up will occur at 4 weeks (+/- 1 week) and 3 months (+/- 2 weeks) at which times all follow-up measures will be obtained. All patients will follow-up with the primary investigator who performed the injection.

This study is intended to compare outcomes at 2-4 weeks and 3 months following an initial sacroiliac joint steroid injection. The patient's first injection will define the study start date and the outcome assessment timeline for that respective patient. During the 3 months from this start date, a participant may receive one additional injection per protocol, at which point the follow-up schedule will revert back to the beginning, starting with the 4 week time point and continuing up to the final 3-month follow-up. Repeat injection will be with the same steroid the patient initially randomized to. Only one additional injection is allowed within the protocol.

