### **Specific Aims:**

1. Compare the proportion of patients between groups with a good response (80% or greater improvement in index pain) after sacroiliac joint corticosteroid injection at 2-4 weeks and 3 months.

2. Compare the proportion of patients between groups with a moderate response (50% or greater improvement in index pain) after sacroiliac joint corticosteroid injection at 2-4 weeks and 3 months.
3. Compare the proportion of patients between groups who have at least 30% improvement in ODI at 2-4 weeks and 3 months
4. Compare the proportion of patients between groups who have ODI score less than 20% at 2-4 weeks and 3 months.
5. Compare the proportion of patients between groups who had a good response at 2-4 weeks that continue to have good response at 3 months
6. Compare the proportion of patients between groups who had a good response at 2-4 weeks that continue to have at least moderate response at 3 months.
7. Compare the number of patients who have at least moderate response at 2-4 weeks who require repeat injection prior to 3 months.
8. Compare the number of patients with cessation of pain medication use, other than over-the-counter medication, for index pain at 2-4 weeks and 3 months
9. Report Adverse Events

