#### **Repeat Injection Criteria:**

An patient who achieves at least 80% relief immediately after the injection and subsequently reports less than moderate relief (<50% relief on NPRS) at any point in the study will be offered repeat sacroiliac joint steroid injection. Repeat injection will be performed on the same side(s) as the initial injection and with the same steroid the patient was initially randomized to. If any additional injections are deemed warranted by the treating physician the patient will be considered a treatment failure in the study.

**Injection:** Unilateral or bilateral Injection will be allowed at the discretion of the treating physician.

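### The visit schedule restarts after a repeat injection, so a re-injected patient loses the first-injection 3-month score, and no section says how that patient is scored

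*Combined protocol and SAP*

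**What the plan says.** The Follow-up section of the Study Timeline states the aim: "This study is intended to compare outcomes at 2-4 weeks and 3 months following an initial sacroiliac joint steroid injection". It adds that the patient's "first injection will define the study start date and the outcome assessment timeline". Visits are set at 4 weeks (give or take 1 week) and 3 months (give or take 2 weeks). The sentence after the one on the timeline permits one repeat injection, "at which point the follow-up schedule will revert back to the beginning, starting with the 4 week time point", with follow-up then running to a final 3-month visit.

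Repeat Injection Criteria offers the repeat to a patient who had at least 80% immediate relief and then "reports less than moderate relief (<50% relief on NPRS) at any point in the study will be offered repeat sacroiliac joint steroid injection". The repeat uses the same steroid.

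Primary Outcomes defines success as at least 50% NPRS improvement, with 2-4 weeks as the primary time point. It lists response at 3 months (item 1) and the number of injections needed to reach response at 3 months (item 2) as other comparisons. Specific Aims 5 and 6 concern patients "who had a good response at 2-4 weeks that continue to have good response at 3 months" and those "who had a good response at 2-4 weeks that continue to have at least moderate response at 3 months". Aim 7 counts early responders who need a repeat before 3 months. Hypothesis and Analysis both name 3 months alongside 4 weeks.

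**The concern.** For a re-injected patient, the two statements in Follow-up give different assessment dates and different exposures: one injection or two. The repeat trigger is the complement of the success definition, so the affected patients are selected on outcome and are not a random subset.

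Two analysts could therefore score the same patient differently at 3 months, and the two scorings answer different questions. One is the effect of the first injection. The other is the effect of up to two injections of the assigned steroid. Aims 5 and 6 show the problem most clearly: a patient who responded at 4 weeks, relapsed, was re-injected and recovered could be counted as having kept the response throughout. Without a written rule, the choice could be made after results are seen.

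**Working it through.** The plan gives no figure on this point to reproduce. The check is of dates, then text, then an illustration.

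**1. Dates.** Assumption: 3 months is 13 weeks. The original windows are then weeks 3-5 and 13 ± 2 = weeks 11-15. A repeat at week w puts the restarted visits nominally at w + 4 and w + 13.

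| Repeat at week | Restarted 4-week visit | Restarted 3-month visit | First-injection score lost |
|---|---|---|---|
| 2 | 6 | 15 | 4-week and 3-month |
| 4 | 8 | 17 | 3-month |
| 6 | 10 | 19 | 3-month |
| 7 | 11 | 20 | 3-month |
| 11 | 15 | 24 | 3-month |

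The rows for weeks 4 to 11 assume that the original 4-week visit has taken place. After a repeat at weeks 4-6, neither restarted visit falls nominally in the original 3-month window. After a repeat at weeks 7-11, the restarted 4-week visit does, so one post-repeat score could be read as either time point.

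**2. Is there a scoring rule anywhere?**
- Data Analysis covers descriptive statistics and baseline comparisons only.
- Analysis names intention to treat and no crossover. Neither helps, because the repeat is the same steroid.
- Aim 7 counts some repeats but does not score them.
- Primary Outcomes item 1 does not say from which injection 3 months runs. Item 2 presupposes that response after a second injection can count. Aims 5 and 6 need the first-injection course.
- The treatment-failure sentence in Repeat Injection Criteria concerns injections beyond the one repeat (see the objection).

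Nothing says whether the patient is a non-responder, is scored at the restarted visit, or is treated as missing. Keeping the last pre-repeat score is also possible. For the 50% NPRS outcome it gives the same answer as non-response, since that score is below 50% by the trigger.

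**3. Illustration of what the choice can do.** Inputs: 51 per arm less 15% loss (Power Analysis), 51 × 0.85 = 43; first-injection rates of 70% vs 50% or 50% vs 30%, from the plan's 50% reference and 20-point target. Assumed: uptake u of 50% or 100%; second response q of 30%, 50%, or equal to the arm's own first rate.

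If post-repeat scores count, observed rate = p + (1 − p)·u·q. Power at one time point, two-sided 0.05, with p̄ the mean of the two rates:

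Φ{[d − 1.96·√(2p̄(1 − p̄)/n)] / √([p1(1 − p1) + p2(1 − p2)]/n)}

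Without repeats, 70% vs 50%: (0.20 − 1.96 × 0.1056)/0.1034 = −0.07, power 0.473. The result is the same for 50% vs 30%.

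| First rates | u | q | Observed rates (%) | Difference (points) | Power |
|---|---|---|---|---|---|
| 70/50 | 50% | 30% | 74.5/57.5 | 17 | 0.382 |
| 70/50 | 50% | 50% | 77.5/62.5 | 15 | 0.327 |
| 70/50 | 50% | own | 80.5/62.5 | 18 | 0.455 |
| 70/50 | 100% | 30% | 79/65 | 14 | 0.301 |
| 70/50 | 100% | 50% | 85/75 | 10 | 0.210 |
| 70/50 | 100% | own | 91/75 | 16 | 0.506 |
| 50/30 | 50% | 30% | 57.5/40.5 | 17 | 0.349 |
| 50/30 | 50% | 50% | 62.5/47.5 | 15 | 0.285 |
| 50/30 | 50% | own | 62.5/40.5 | 22 | 0.533 |
| 50/30 | 100% | 30% | 65/51 | 14 | 0.257 |
| 50/30 | 100% | 50% | 75/65 | 10 | 0.170 |
| 50/30 | 100% | own | 75/51 | 24 | 0.639 |

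The smallest rise in an arm's rate is 74.5 − 70 = 4.5 points and the largest is 65 − 30 = 35 points.

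Leaving re-injected patients out also changes the result. At 70/50 and u = 50%: 0.70/0.85 = 82.4%, 0.50/0.75 = 66.7%, a difference of 15.7 points.

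Unequal uptake can create a difference where there is none. With both first rates 50% and q = 50%, uptake of 60% vs 40% gives 65% vs 60%, a 5-point difference (rejection about 8%).

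**4. Aim 6.** If a share l of good responders falls below 50% relief and all are re-injected, the apparent rate is 1 − l + l·q. For l = 20% it reads 86% (q = 30%) to 90% (q = 50%) instead of 80%. For l = 40% it reads 72% to 80% instead of 60%.

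**The case against.** **The failure rule already settles it.** Repeat Injection Criteria says: "If any additional injections are deemed warranted by the treating physician the patient will be considered a treatment failure in the study". A reader might infer that this covers the first repeat, or that it is seriously ambiguous. The documents do not support that. Follow-up permits one repeat within the protocol, the sentence comes after the repeat has been described, and counting the injections needed to respond (Primary Outcomes item 2) would be empty if the first repeat were already a failure. The sentence means injections beyond the one repeat, so it leaves the re-injected patient unscored.

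**The final 3-month visit may mean the original one.** This is possible, although a schedule that returns to its beginning points the other way. Even so, the score would follow two injections, with no rule for using it.

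**A strategy of up to two injections was intended.** A permitted same-steroid repeat, intention to treat, the pragmatic label and item 2 all fit that question. This part stands: it is a legitimate comparison and should be kept. It does not displace the stated intention to compare outcomes after the initial injection, or Aims 5 and 6 on maintained response.

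**The numbers are assumptions.** This also stands. Uptake and second response are not in the documents, and the 50% reference rate is not shown to hold in patients selected on 80% immediate relief. The power figures are for one time point and are not the power of the planned repeated-measures model.

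**Conclusion.** The point holds. The schedule rule conflicts with the plan's own stated question, and no section repairs it for patients who are selected on outcome. This follows from the text alone.

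The exposure is mainly the 3-month response and Aims 5 and 6. A reader might infer that the primary outcome is undermined. It is largely protected, and is exposed only by repeats given before the 4-week visit or if a restarted 4-week score is substituted. Nor can a bias towards either steroid be claimed. In the assumed scenarios a 20-point difference becomes anything from 10 to 24 points, and power of 47% becomes 17% to 64%, so the effect can go either way. These ranges illustrate why a rule is needed and do not estimate what will happen. The matter should be fixed before analysis.

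**What to change.** Reconcile Follow-up, Repeat Injection Criteria, Primary Outcomes and Analysis, in line with the stated aim:

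- Time the 4-week and 3-month responder outcomes from the first injection. This covers NPRS response and the binary ODI and medication outcomes (Aims 1-6 and 8).
- Count a patient re-injected before an assessment as a non-responder at that assessment. A repeat given at the 4-week visit, after scoring, affects the 3-month assessment only.
- Report results on the restarted schedule, including Primary Outcomes item 2, as a separate comparison labelled as one or two injections of the assigned steroid.
- If ODI is also analysed as a score, state how post-repeat values are handled, since a non-responder rule cannot supply one.
- Record the date of the repeat, and report repeat counts by arm over all randomised patients.
- Optionally, word the failure sentence as applying beyond the one repeat, to match Follow-up.

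Who is offered a repeat, and when, is unchanged. The responder outcomes need no added visit. The cost is a few sentences and one form field. If post-repeat responses would otherwise have been counted, reported 3-month response rates fall by 4.5 to 35 points per arm in the assumed scenarios.
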